5.7 Administration and Accountability

N/A.

5.7.1 Return or Destruction of Investigational Product

N/A.

6 Study Procedures

[figure not shown]
CONFIDENTIAL

This material is the property of the University of Pennsylvania.

TABLE 1: SCHEDULE OF STUDY PROCEDURES

Study Phase	Screening	Intervention: Ablation	Visit 1	Visit 2
Visit Number		0	6 weeks	6 months
Informed Consent/Assent	X			
Review Inclusion/Exclusion Criteria	X			
Demographics/Medical History	X			
Physical Examination	X		X	X
Vital Signs: BP, HR, RR	X	X	X	X
Height and Weight	X	X		
Randomization		X		
Adverse Event / Unanticipated Problems Assessment		X	X	X
12-Lead ECG	X	X	X	X
30-day Monitor		X		X

Figure 1. Study flowchart

CONFIDENTIAL

This material is the property of the University of Pennsylvania.

6.1 Study Intervention Phase

6.1.1 Baseline visit

- Physical Exam
- Vital Signs
- Height and Weight
- Medical Records Review
- Review Inclusion/Exclusion Criteria
- Informed consent

6.2 Follow Up Phase of the Study

6.2.1 Visit 1 (6 weeks)

- Physical Exam
- Vital Signs
- Medical Records Review
- Assess possible adverse events
- Consider stopping anti-arrhythmic drug if continued post procedure
- 12 lead ECG

6.2.2 Visit 2 – End of Study Visit (6 months)

- Physical Exam
- Vital Signs
- Medical Records Review
- Assess possible adverse events
- 30 day monitor
- 12 lead ECG

6.3 Unscheduled Visits

Subjects may experience unanticipated problems, complications or intolerable symptoms such as palpitations, dyspnea after ablation, unscheduled visits may occur. Physical examination, 12-lead ECG, medical treatment, and complication management may be applied for the study subjects. If subjects have severe condition, admission will be arranged.

6.4 Subject Withdrawal

Participants may be withdrawn if failure to adhere to protocol requirements is noted, or if the participant wishes to and consents to withdrawal.

7 Study Evaluations and Measurements

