5.2 Intervention Regimen

In the investigational group, distal coronary sinus pacing will be utilized to localize the earliest connection (aside from septal) from the coronary sinus to the left atrial musculature. Once localized focal radiofrequency lesions will be applied at the discretion of the investigator until central (septal) activation of the left atrium is noted during distal coronary sinus pacing.

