5.6 Blinding

The unblinded research coordinator will keep a master file of participant assignments. Once a participant is randomized, the investigator/clinician for the patient will be notified of the participant assignment. The remainder of the research team and the participant will be blinded to participant assignment.

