10.1 Confidentiality

Information about study subjects will be kept confidential and managed according to the requirements of the Health Insurance Portability and Accountability Act of 1996 (HIPAA). Those regulations require a signed subject authorization informing the subject of the following:

- What protected health information (PHI) will be collected from subjects in this study
- Who will have access to that information and why
- Who will use or disclose that information
- The rights of a research subject to revoke their authorization for use of their PHI.

In the event that a subject revokes authorization to collect or use PHI, the investigator, by regulation, retains the ability to use all information collected prior to the revocation of subject authorization. For subjects that have revoked authorization to collect or use PHI, attempts should be made to obtain permission to collect at least vital status (i.e. that the subject is alive) at the end of their scheduled study period.

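### Section 6.4 allows withdrawal for non-adherence and does not say that outcome follow-up continues, so primary-endpoint data can be lost selectively

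*Combined protocol and SAP*

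**What the plan says.** Section 6.4 gives two grounds for leaving the study. The first is non-adherence: "Participants may be withdrawn if failure to adhere to protocol requirements is noted". The second is the participant's own choice. It says nothing further about what counts as failure, who makes the decision, whether that person is blinded, or what is collected afterwards.

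Other sections bear on this:

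- **Analysis set.** Section 8.5 analyses randomized participants only if they have not withdrawn. The Study Summary describes the primary efficacy analysis as intent-to-treat.
- **Who knows the arm.** Section 5.6 states: "Once a participant is randomized, the investigator/clinician for the patient will be notified of the participant assignment". It also states: "The unblinded research coordinator will keep a master file of participant assignments". Everyone else is covered by "The remainder of the research team and the participant will be blinded to participant assignment". Sections 3.1.3 and 7.5 add two blinded electrophysiologists to adjudicate events.
- **Arm-specific procedure.** Section 5.2 has Group 2 lesions delivered, at the investigator's discretion, "until central (septal) activation of the left atrium is noted during distal coronary sinus pacing".
- **Endpoint window and schedule.** Sections 3.2.1 and 8.1 count recurrence only after the 90-day blanking period. Scheduled rhythm checks after ablation are a first-month monitor, a 6-week ECG, a last-month monitor and a 6-month ECG (Sections 3.1, 3.1.3, 6.2 and Table 1).
- **Data after exit.** Section 10.1 asks for permission to collect at least vital status, and only from those who revoke authorization. Sections 8.4.3 and 9.2 promise adverse-event data on all randomized subjects, and recording of all adverse events in the study period.

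**The concern.** In a drug trial, withdrawal for non-adherence at least stops a treatment. Here the treatment is over once the ablation ends, so withdrawing someone later changes nothing except whether the outcome is seen. People who miss visits or wear the monitor poorly may differ in recurrence risk from those who comply. If they are removed, the loss is potentially informative, and neither the log-rank test nor the Cox model corrects for it.

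Two features make this more than a formality. First, two unblinded roles are close to each patient, and Section 6.4 does not stop either from influencing the decision. Blinded adjudication protects the reading of recorded events, not the decision to stop recording them. Second, the trial is small: about 18 events are expected at the design hazard ratio, so a handful of lost patients matters. Section 8.3 makes no allowance for dropout, and no missing-data method or sensitivity analysis is given.

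**Working it through.** **1. What a withdrawn participant still contributes.** The first monitor ends near day 30 and the interim ECG is at 6 weeks (about day 42). Both fall before day 90. The next scheduled rhythm checks are the last-month monitor and the 6-month ECG. A participant withdrawn before those has no scheduled observation in the endpoint window. Correcting Section 8.5 alone would not create the missing data: someone censored before day 90 adds nothing to a comparison that starts at day 90.

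**2. The plan's own figure.** Inputs from Section 8.3: 100 participants randomized 1:1, control freedom 0.7, two-sided alpha 0.05, power 0.80, hazard ratio (HR) 0.2, log-rank test.

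- Expected events = 50 × 0.30 + 50 × (1 − 0.7^0.2) = 15 + 3.4 = 18.4.
- Freedman's formula needs (1.960 + 0.842)² × (1.2/0.8)² = 17.7, so 18 events.
- Power = Φ(√18.4 × 0.8/1.2 − 1.960) = 0.817.

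The stated HR of 0.2 therefore reproduces, with no margin for loss.

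**3. Loss unrelated to outcome (assumed rates).** Scaling the expected events and applying the same power formula:

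| Removed | Events at HR 0.2 | Power |
|---|---|---|
| 0% | 18.4 | 0.817 |
| 5% | 17.5 | 0.797 |
| 10% | 16.6 | 0.775 |
| 20% | 14.8 | 0.726 |

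**4. Selective loss from one arm, no true effect (assumed pattern).** Take 50 per arm and 30% recurrence in both, so 15 expected recurrences in each arm. Assume that n Group 2 patients are removed and that their recurrence risk is 60%. The remaining Group 2 risk is p = (15 − 0.6n)/(50 − n), and the apparent HR is ln(1 − p)/ln(0.7).

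| n | p | Apparent HR |
|---|---|---|
| 3 | 13.2/47 = 28.1% | 0.92 |
| 5 | 12/45 = 26.7% | 0.87 |
| 10 | 9/40 = 22.5% | 0.71 |

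Under these assumptions, a log-rank simulation (20,000 runs) gives two-sided false-positive rates of about 5.7%, 6.1% and 11.8% for n = 3, 5 and 10, against 5.2% with none removed.

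**5. A harsher assumption.** Suppose every patient removed from one arm would have recurred. Simulation (8,000 runs) then gives the following, against 5.0% with none withdrawn:

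| Mean number withdrawn | False-positive rate if excluded | If censored |
|---|---|---|
| 3 | 7.4% | 8.6% |
| 4.5 | 11.7% | 14.6% |

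Censoring does not repair the bias.

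The calculation in step 4 takes patients out of the denominator, which is also what Section 8.5 does. The figures show the joint effect of Sections 6.4 and 8.5 and cannot be credited to 6.4 alone.

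**The case against.** The strongest reply is that Section 6.4 is standard permissive wording in a single-center pilot, and that the documents do not show it would work differently by arm. Much of this stands, and it rules out three stronger readings that a reader might infer.

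- **That Group 2 patients whose connection was not eliminated will be removed.** Septal activation is an operator's endpoint, pursued at the investigator's discretion. It is not something a participant adheres to. Group 1 has procedural requirements too: pulmonary vein isolation and elimination of other triggers. Treating an unmet procedural endpoint as non-adherence is one possible reading that 6.4 leaves open. Missed visits and poor monitor wear can occur in either arm, among blinded participants.
- **That the plan forbids follow-up after withdrawal, or limits it to vital status.** Section 6.4 is silent. The Section 10.1 clause sets a minimum and applies only to revoked authorization. Section 10.2 draws study data from the medical record, and Section 7.5 counts symptom-prompted ECGs. Some events could be recovered, but nothing requires it after withdrawal.
- **That the 30-day safety composite loses anyone withdrawn early.** Sections 8.4.3 and 9.2 promise otherwise. The fair criticism is that 6.4 is not reconciled with that promise.

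It is also fair that the bias is modest under the milder assumption unless about 10 of 50 patients are removed from one arm. What the objection does not answer is that non-adherence alone is a stated ground for withdrawal, that no section continues rhythm follow-up, and that Section 8.5 drops those withdrawn.

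**Conclusion.** The point holds as a weakness in the written rules, not as a prediction of bias. Followed as written, Sections 6.4 and 8.5 allow outcome data to be lost for reasons that may be related to outcome, with two unblinded roles in a position to influence who is withdrawn. That Section 6.4 leaves the decision with either of them is an inference, because it names no one.

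The size is uncertain, since the documents give no withdrawal rate. Under no true effect and an assumed 60% risk in those removed, the apparent HR runs from about 0.92 (3 removed) to 0.71 (10 removed, which is 20% of Group 2). That is small beside the design HR of 0.2, but all of it is spurious. Outcome-neutral loss of 10% costs about 4 points of power (0.817 to 0.775). The case for changing the text rests on how cheaply the gap can be closed.

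**What to change.** - **Section 6.4.** Remove non-adherence as a ground for withdrawal from the study. Record it as a protocol deviation, including an unmet procedural endpoint in either arm. Keep the participant in scheduled follow-up to 6 months.
- **Section 8.5.** Analyse these participants as randomized, in line with the Study Summary.
- **Participant's own request to leave.** Seek permission to go on collecting arrhythmia and adverse-event data from the health record to month 6. Extend the Section 10.1 request beyond vital status to match.
- **Safety.** Reconcile 6.4 with Section 8.4.3, so that the promise of adverse-event data on all randomized subjects explicitly covers anyone who leaves.

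An extra monitor at the time of withdrawal is not a substitute. Fitted at the 6-week visit, it would run from about day 42 to day 72, inside the blanking period, and it is not in Table 1.

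The cost is a few sentences, one consent-form line, and chart follow-up of a few non-adherent participants. No study procedure is added.

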7.1 Medical Record Review

The following variables will be abstracted from the medical chart:

- *Date of birth*
- *Height*
- *Weight*

CONFIDENTIAL

This material is the property of the University of Pennsylvania.

- *History of co-morbidities related to AF including obstructive sleep apnea, hypertension, and thyroid disorders.*
- *Any history of prior cardiovascular disease*
- *Cardiovascular imaging details including echocardiography, CT angiography, or cardiovascular MR imaging*

7.2 Physical Examination

Standard cardiovascular physical examinations will be performed at study enrollment, on the date of ablation and during the 2 follow-up visits.

7.3 Vital Signs

Standard vital signs at clinic visits will be recorded. No study related changes to routine measurements will be made.

7.4 Laboratory Evaluations

N/A

7.5 Efficacy Evaluations

12 lead ECGs obtained at clinic visits, and as prompted by symptoms, as well 30 day monitors immediately following AF ablation and at 6 months will be utilized for efficacy assessment. Two electrophysiologists that will be blinded to study assignments will adjudicate the AF ECG data. Time to first AF episode (following ablation) and AF burden (following ablation) will be ascertained.

7.6 Safety Evaluations

Comparing study adverse outcomes between the two study groups will be utilized to assess the safety of the additional ablation lesions in the investigational arm.

8 Statistical Plan

8.1 Primary Endpoint

The primary endpoint is the recurrence of atrial arrhythmia post-ablation. The primary endpoint is defined as a non-self-terminating (>30 seconds) episode of atrial fibrillation, atrial flutter, or atrial tachycardia demonstrated by ECG or 30 day monitors after the 90-day post-ablation blanking period.

8.2 Secondary Endpoints

The secondary endpoint will be AF burden on the immediate post ablation and 6-month 30-day monitors.

8.3 Sample Size and Power Determination

Assuming alpha 0.05, power 0.80, and 1:1 randomization of 100 participants, and 0.7 probability of AF freedom in the control group, we will resolve a 2-sided minimum experimental arm hazard ratio of 0.2 with implementation of the log-rank test.

8.4 Statistical Methods

Descriptive summaries of baseline clinical and demographic characteristics will be provided by randomized treatment assignment for each analysis population. Cumulative incidence curves for the first atrial arrhythmia recurrence will be constructed by randomization group and compared via log rank and proportional hazard models.

CONFIDENTIAL

This material is the property of the University of Pennsylvania.

8.4.1 Baseline Data

Baseline and demographic continuous variables will be summarized as mean+standard deviation (SD). Categorical variables will be expressed as standard percentages.

8.4.2 Efficacy Analysis

Cumulative incidence curves for the first atrial arrhythmia recurrence and for death will be constructed by randomization group and compared using log rank and proportional hazard methods.

8.4.3 Safety Analysis

All subjects entered into the study and randomized at the baseline visit will have detailed information collected on adverse events for the overall study safety analysis

8.5 Subject Population(s) for Analysis

Data from all participants that are randomized into the study will be analyzed as long as the participants does not withdraw from the study.

9 Safety and Adverse Events

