LA: Left atrial

CONFIDENTIAL

This material is the property of the University of Pennsylvania.

Study Summary

Title	Prospective Elimination Of Distal Coronary Sinus-Left Atrial Connections for Atrial Fibrillation Ablation Trial
Short Title	PRECAF Trial
IRB Number	
Protocol Number	
Phase	Pilot Study.
Methodology	Randomized; Single blind.
Study Duration	2 years
Study Center(s)	Single-center
Objectives	To examine the efficacy of targeting connections between coronary sinus and left atrium during an ablation procedure in addition to pulmonary vein (PV) isolation and non-PV triggers in Atrial fibrillation patients.
Number of Subjects	100 subjects are expected to be enrolled. An interim analysis will be performed after enrollment of 50 patients.
Main Inclusion and Exclusion Criteria	
Inclusion criteria are:
 
● Patients with paroxysmal or persistent atrial fibrillation; AND● Undergoing first AF ablation; AND● Age ≥ 18 years. 
Patients are not eligible if they have any of the following exclusion criteria:
 
● Previous left atrial ablation;● Women currently pregnant;● Mental or physical inability to take part in the study;● Known terminally ill patients.

Investigational Product (drug, biologic, device, etc.)	
For Device include the planned use	N/A
For Drug, food, cosmetic, etc. include the dose, route of administration and dose regimen	N/A
Duration of administration (if applicable)	N/A
Reference therapy	The reference therapy is pulmonary vein isolation and elimination of non-PV triggers. The investigational arm will include pulmonary vein isolation and non-PV trigger elimination, in addition to distal coronary sinus isolation.
Statistical Methodology	The primary efficacy analysis will be performed among the intent-to-treat study groups using Cox-regressions and Kaplan-Meier curves to compare time to the initial occurrence of AF after the blanking period following AF ablation.
Safety Evaluations	
Occurrence of one or more of the following events during the 30 day period following the ablation procedure:
 
 1. stroke, 2. myocardial infarction, 3. esophageal injury, 4. pulmonary vein stenosis, 5. bleeding, 6. heart failure, and 7. death.

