3.1 General Design

The study is designed as a randomized, single-blind, small scale pilot study. Expected duration of subject participation is six months. A 30-day event monitor will be used for the first month after ablation. Then, regular clinic visits at 6 weeks and 6 months will be arranged after ablation with 12 lead electrocardiogram check-up. In the last month, a 30-day event monitor will be set to detect the recurrence of atrial arrhythmias.

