3.1.3 Follow Up Phase

A 30-day event monitor will be used for the first month after ablation. Then, regular clinic visits at 6 weeks and 6 months will be arranged after ablation with 12 lead electrocardiogram check-up. In the last month, a 30-day event monitor will be set to detect the recurrence of atrial arrhythmias. An adjudication committee consisting of two electrophysiologists that are blinded to the randomization scheme will review AF events. Time to first AF episode will be recorded as the primary outcome.

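### Section 8.5 analyses randomized participants only if they do not withdraw, which on its plain reading conflicts with the Summary's intent-to-treat primary analysis; no censoring rule is given and the size of the effect cannot be judged

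*Combined protocol and SAP*

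**What the plan says.** Two places bear directly on who is in the primary efficacy analysis.

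- Study Summary, Statistical Methodology: "The primary efficacy analysis will be performed among the intent-to-treat study groups".
- Section 8.5: "Data from all participants that are randomized into the study will be analyzed as long as the participants does not withdraw from the study".

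Section 8.4.2 agrees with the Summary: "Cumulative incidence curves for the first atrial arrhythmia recurrence and for death will be constructed by randomization group". Section 8.4 mentions more than one analysis population, but only 8.5 describes any.

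On withdrawal, section 6.4 allows it at the participant's wish and also says "Participants may be withdrawn if failure to adhere to protocol requirements is noted". Under section 5.6, once a participant is randomized, "the investigator/clinician for the patient will be notified of the participant assignment"; the rest of the research team and the participant stay blinded. Section 3.1.3 adds "An adjudication committee consisting of two electrophysiologists that are blinded to the randomization scheme will review AF events".

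On timing, section 8.1 counts a recurrence if it is "demonstrated by ECG or 30 day monitors after the 90-day post-ablation blanking period". The 6-week visit falls inside that blanking period. The next planned rhythm check is in section 3.1: "In the last month, a 30-day event monitor will be set to detect the recurrence of atrial arrhythmias". Section 7.5 also uses ECGs prompted by symptoms. Section 4.4 ends participation at 6 months.

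No section gives a withdrawal rate, a censoring rule for withdrawn participants, a missing-data method or a sensitivity analysis.

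**The concern.** Withdrawal happens after randomization. A rule that removes people because of it is not intent-to-treat, whatever the analysis is called. Taken literally, 8.5 removes a participant who has a documented recurrence on day 120 and withdraws on day 150, and the recurrence goes too.

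Two things are at stake. First, two different primary populations could both be called pre-specified once the data are seen. Second, the comparison would depend on who stays in the study, and that may be related to arm or outcome. Blinded adjudication protects how an event is classified. It does not protect who remains in the analysis.

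**Working it through.** **Inputs.** From section 8.3: 100 participants randomized 1:1 (50 per arm), two-sided alpha 0.05, power 0.80, control AF freedom 0.7, hazard ratio (HR) 0.2, log-rank test. From 8.1 and 4.4: events count from day 90 and follow-up ends at 6 months. Withdrawal rate and timing are not given, so all deletion patterns below are assumptions.

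**1. The plan's own figure.** Experimental freedom is 0.7^0.2 = 0.931. Expected events are 50 × 0.30 = 15 control and 50 × 0.069 = 3.4 experimental, 18.4 in total. Freedman's formula gives ((1 + 0.2)/(1 − 0.2))² × (1.96 + 0.84)² = 2.25 × 7.85 ≈ 18 events. Power at 18.4 events is Φ(√18.4 × 0.8/1.2 − 1.96) = 0.817. The stated HR of 0.2 at 80% power is reproduced.

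**2. Deleting observed recurrences.** Log-rank p depends on event order, so each row averages simulated draws with event times uniform on days 90–180 and everyone else censored at day 181. The last column is the pooled two-proportion z, which can be checked by hand.

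| Control v experimental | Change | Mean p | z |
|---|---|---|---|
| 15/50 v 4/50 | near planned effect | 0.005 | −2.80 |
| 14/49 v 4/50 | one control recurrence deleted | 0.008 | −2.65 |
| 15/50 v 3/49 | one experimental recurrence deleted | 0.002 | −3.08 |
| 10/45 v 4/50 | five control recurrences deleted | 0.052 | −1.95 |
| 15/50 v 7/50 | weaker effect | 0.055 | −1.93 |
| 15/50 v 6/49 | one experimental recurrence deleted | 0.032 | −2.16 |
| 15/50 v 6/50 | weaker effect | 0.029 | −2.21 |
| 13/48 v 6/50 | two control recurrences deleted | about 0.06 | −1.89 |

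Cox HRs for the first three rows are 0.236, 0.250 and 0.179. For 15/50 v 7/50 and 15/50 v 6/49 they are 0.426 and 0.369. Seven experimental events is roughly what a true HR of 0.4 would give: 50 × (1 − 0.7^0.4) = 6.6.

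The mean p hides some spread. At 15/50 v 7/50, 26–27% of draws are already below 0.05, and at 10/45 v 4/50 about 39% still are. The threshold crossings are therefore typical, not certain.

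**3. Selective deletion with no true effect.** Take 30% recurrence in both arms and use the two-proportion z as an approximation. Deleting 20% of experimental recurrences (0.20 × 15 = 3 people) raises two-sided type I error from 0.049 to 0.080. Deleting 33% (about 5 people) raises it to 0.134. These rates are illustrations, not predictions.

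**4. Withdrawals with no recurrence.** No primary event can occur before day 90, so anyone who leaves earlier is never in a risk set. Excluding or censoring such participants gave identical HR and p in every draw. With five event-free withdrawals after day 90 in one arm, the HR is 0.221 censored v 0.209 excluded (control arm) or 0.250 v 0.264 (experimental arm).

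**5. Exclusion unrelated to arm or outcome.** Freedman power falls from 0.817 to 0.797, 0.775 or 0.726 if 5%, 10% or 20% are excluded. Type I error stays near 0.05.

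**The case against.** The strongest reply is that 8.5 can be read temporally, with data used for as long as the participant stays in. The Summary speaks specifically about the primary efficacy analysis and could be taken to govern a general sentence about all data. That reading is possible, and it would remove most of the conflict. But nothing states it, and without a censoring rule it could not be programmed from the text.

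A second reply is that the schedule leaves little to delete. With no planned rhythm check between day 90 and the last-month monitor, an observed recurrence would come mainly from a symptom-prompted ECG, an unscheduled visit or that last monitor. This is fair, and a reader might infer that the effect is limited. The documents do not support that conclusion, because it needs a withdrawal rate and mechanism and they give neither.

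A reader might equally infer that the unblinded clinician will remove participants selectively. That is not supported either: 6.4 does not say who decides on withdrawal, and 5.6 does not link the clinician to the decision. Outcome-related exclusion is possible, not shown.

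It is also true that section 10.1 concerns revoked privacy authorization, not study withdrawal. It supports keeping earlier data only by analogy.

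**Conclusion.** The concern stands as a rule that is wrong as written. On its plain reading, 8.5 conflicts with the Summary's intent-to-treat analysis and with 8.4.2, and nothing in the documents supplies the censoring rule that the milder reading needs. It should be fixed, ideally before any outcome data are seen.

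No expected bias can be stated. Near the planned effect the conclusion is robust to one deletion, and losing significance takes about five control deletions. Near the threshold, one or two deletions can be enough, in either direction. All of this rests on assumed deletion patterns and simulated event times.

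The finding that withdrawals before day 90 make no difference applies to the primary endpoint only. It does not extend to AF burden on the first monitor (8.2) or the 30-day safety composite (3.2.3), which use earlier data. For safety, 8.4.3 already provides for adverse event information on all randomized subjects, but 8.5 contains no exception for it.

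**What to change.** Reword 8.5 to say:

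- All randomized participants are analysed in their assigned arm.
- Data collected up to withdrawal are used. A recurrence after day 90 and before withdrawal counts as an event; otherwise time is censored at the last rhythm assessment.
- Withdrawal or non-adherence under 6.4 does not by itself remove a participant from the analysis.
- Withdrawals, and participants with no rhythm assessment after day 90, are reported by arm.
- Any analysis that excludes withdrawals is a sensitivity analysis only.

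The cost is a few sentences and a little more analysis and reporting work, with no extra patients or visits. The change does not recover follow-up lost to early withdrawal. It removes the conflict and keeps recurrences that were already observed.
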